4.3 Exclusion criteria

- Allergy to hydroxychloroquine or azithromycin
- History of bone marrow transplant
- Known G6PD deficiency
- Chronic hemodialysis or glomerular filtration rate < 20ml/min
- Psoriasis
- Porphyria
- Concomitant use of digitalis, flecainide, amiodarone, procainamide, propafenone, cimetidine, dofetilide, phenobarbital, phenytoin, or sotalol
- Known history of long QT syndrome
- Current known QTc>500 msec
- Pregnant or nursing
- Prisoner
- Weight < 35kg
- Seizure disorder
- Severe liver disease
- Outpatient use of hydroxychloroquine for treatment of a disease other than COVID-19 OR has received more than 2 days of hydroxychloroquine or azithromycin for suspected or confirmed COVID-19
- Patient has recovered from COVID-19 and/or is being discharged from the hospital on day of enrollment.
- Treating physician refuses to allow patient participation in the study
- Unable to obtain informed consent
- Prior enrollment in this study

Severe liver disease is defined as clinical diagnosis of cirrhosis plus presence or history of ascites, varices, hepatic encephalopathy, or hospital admission for liver failure.

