5.0 Study Procedures

Note that given the high contagiousness of SARS-CoV-2, the limited supply of personal protective equipment, and risk to coordinators' health, study visits, procedures, and monitoring will be performed in a no-touch mode. This also applies to the consenting process, which will be performed via a consenting mechanism that confirms the identity of the patient, provides access to the consent form, and obtains a signature to complete documentation, without requiring physical proximity of research staff and the study subject.

5.1 Study commencement. After informed consent and enrollment, coordinators will complete the baseline CRF, and initiate study procedures, including randomization (variable permuted block randomization by hospital).

5.2 Study drug. This is an open label, randomized, active comparator trial. Patients who are discharged home will not continue treatment after hospital discharge. If the patient has already received azithromycin or hydroxychloroquine prior to randomization (no more than 2 days), the prior doses will count toward the 5-day total dose. For enrolled patients whose laboratory testing returns negative for SARS-CoV-2, if the clinical team believes that another cause of the patient's presentation is more likely than COVID-19 in light of the negative laboratory testing, the clinical team may stop study drug. Such discontinuation will be recorded. Since the fundamental clinical question is whether to start treatment in patients with suspected or confirmed COVID-19, these patients will remain in the primary analytic cohort.

The trial will be temporarily suspended for enrollment at a given site in the event that no study drug is available at that site.

5.2.1. Hydroxychloroquine. Patients in the hydroxychloroquine arm will receive hydroxychloroquine 400mg po BID x 1 day, then 200mg po BID x 4 days³ (dose reductions for weight < 45kg or GFR<50ml/min). For patients < 45kg, doses will be halved. For patients with GFR<50ml/min, the final dose of hydroxychloroquine will not be administered. The drug dose chosen falls at the lower end of doses proposed in various international trials, but it has proven in vitro efficacy, with a ratio of lung tissue trough concentrations to the EC50 (effective concentration to suppress 50% of viral activity) of >20.³ Given in vitro confirmation of the adequacy of the dose and likely superior safety profile at the lower dose, we chose the total dose of 2.4gm over 5 days.

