actually enrolled under that criterion. The ITT population thus simplifies to patients with laboratory-confirmed COVID-19. Summaries of safety outcomes will be performed in the safety population consisting of all patients who receive at least one dose of study medication. In a subgroup of the ITT population, we will compare study endpoints among patients who had not received azithromycin before randomization.

Primary Analysis. The prespecified primary analysis will compare the day 14 assessment of the 8-level COVID Ordinal Outcomes Scale between the randomized hydroxychloroquine and azithromycin groups. We will perform this analysis using a proportional odds logistic regression model (also called an ordinal regression model),² with randomized treatment group as the independent variable. Patient age, comorbidities (dichotomized as either no comorbidities or any comorbidities, with the comorbidities drawn from hypertension, COPD, and the Charlson constituent comorbidities³ (Table 1), and the baseline level of the COVID Ordinal Outcomes Scale will be included in the analysis as covariates. Due to restriction of the cohort to hospitalized patients, the baseline COVID Ordinal Outcomes Scale distribution will include only patients with levels 3 through 7. In a sensitivity analysis, we will include the total amount of pre-randomization azithromycin received as another covariate in the primary model.

Table 1. Charlson Comorbidities

Moderate/Severe Liver Disease
Cerebrovascular Disease (CVD)
Peripheral Vascular Disease (surgical)†
Renal disease
Peripheral Vascular Disease (diagnosis) †
Paralysis (Hemiplegia or Paraplegia)
Dementia

Mild liver disease
Congestive heart failure (CHF)
Chronic Obstructive Pulmonary Disease (COPD)
Diabetes with complications
Diabetes

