Meier curves. Patients who die prior to day 28 are assigned an artificial follow-up time of 28 days censored at that point. This will assign to these patients a worse outcome than any surviving patients, and avoid conflating prolonged hospitalization with death. Descriptively, these time-to-event endpoints will be displayed as median (IQR). If fewer than half of patients meet the event before censoring, we will choose an appropriate quantile (e.g., first quartile) for description and display the proportions with events during the respective weeks of follow-up. For the sake of consistency, we will use the same ordinal regression model with the same prior distribution for the odds ratio as was used for the primary analysis to generate median posterior odds ratios and credible intervals for these endpoints.

Sub-groups. On a purely exploratory level, we will summarize effect variation in sub-groups defined by (a) age \geq 65 years, (b) symptom duration \geq 10 days, (c) in ICU at enrollment, (d) presence of at least one comorbidity, (e) race/ethnicity, and (f) receipt of any clinical azithromycin before enrollment. At early interim analyses, the sample size will be too small to support meaningful statistical inference, and we will limit presentation of results in sub-groups to descriptive summaries using the summary measures described for each outcome above.

Missing Data. We expect fewer than 5% of subjects will have missing data on either the primary or key secondary outcomes listed above. Hence, our primary analyses will be restricted to non-missing observations, without imputation. For the primary outcome, a sensitivity analysis will be performed by applying single imputation. Where daily COVID Ordinal Outcomes Scale scores are missing after hospital discharge, we will use last carried forward with the following modifications—patients discharged to a facility other than home will be classified as “home with limitations” (score 2), and patients found subsequently to be home with limitations will be rated as “home with limitations” from hospital discharge through that follow-up point. Patients who are discharged to home and found to have no limitations at day 14 will be rated as “home without” limitations starting at the time of hospital HAHPS SAP

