descriptively by treatment group. If the baseline QTc is available in at least 80% of participants, an analysis of covariance will be performed to compare follow-up QTc between treatment groups with adjustment for baseline QTc. Otherwise, a 2-sample t-test will be used to compare the follow-up QTc levels.

Table 2 Safety outcomes (measured daily for first five days)
Death unrelated to study drug or procedures
Seizure
Receipt of vasopressors
Atrial or ventricular arrhythmia
Cardiomyopathy
cardiac arrest
Hypoxemia requiring supplemental oxygen
ARDS
Mechanical ventilation
ECMO
Elevated LFTs
Pancreatitis
Acute kidney injury
Renal replacement therapy
Symptomatic hypoglycemia
Hematologic or coagulation events
Cytopenias
Severe dermatologic reaction

Nausea/vomiting
Visual changes
C. diff infection

Concomitant medications

The classes of concomitant medications listed in Table 3 were measured at baseline (before randomization) and through day 5 after randomization. Concomitant medications will be descriptively summarized overall and by treatment group. In addition, some patients in the hydroxychloroquine arm received azithromycin either before or in some cases after randomization. The proportion receiving azithromycin was recorded, and in exploratory summaries, safety outcomes will be displayed in that group as well as in the groups who received only azithromycin or only hydroxychloroquine.

Table 3. Concomitant medications
ACE inhibitors
ARBs
NSAIDs
Glucocorticoids
Immune-suppression
Chloroquine
Hydroxychloroquine
Azithromycin
Zinc
Vitamin C

Interim Monitoring.

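### The SAP's efficacy analyses of prior exposure cover azithromycin only, so its no-prior-azithromycin subgroup can still hold azithromycin-arm patients who had already taken hydroxychloroquine

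*SAP*

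**What the plan says.** **Eligibility and prior doses (Protocol).** Section 4.3 excludes a patient who "has received more than 2 days of hydroxychloroquine or azithromycin for suspected or confirmed COVID-19". Shorter prior treatment with either drug is allowed. Section 5.2 has one rule for both drugs, beginning "If the patient has already received azithromycin or hydroxychloroquine prior to randomization (no more than 2 days"): those doses count toward the 5-day course. Section 4.3 separately excludes "Outpatient use of hydroxychloroquine for treatment of a disease other than COVID-19", with no matching exclusion for azithromycin.

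**Efficacy analyses of prior exposure (SAP).** There are three:

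- Primary Analysis, sensitivity model: "we will include the total amount of pre-randomization azithromycin received as another covariate in the primary model".
- Analysis Sets, restricted subgroup of the ITT population: "we will compare study endpoints among patients who had not received azithromycin before randomization".
- Sub-groups, exploratory item (f): "f) receipt of any clinical azithromycin before enrollment".

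**Descriptive reporting (SAP, Concomitant medications).** "The classes of concomitant medications listed in Table 3 were measured at baseline (before randomization") and through day 5. Table 3 includes hydroxychloroquine, chloroquine and azithromycin, summarized overall and by treatment group. The same section notes that some hydroxychloroquine-arm patients received azithromycin before or after randomization. It plans exploratory safety displays for that group and for patients who received only one of the two drugs.

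**The concern.** In a two-drug comparison, prior exposure can blur the contrast from either side: azithromycin taken by patients later assigned to hydroxychloroquine, or hydroxychloroquine taken by patients later assigned to azithromycin. The protocol permits both on the same terms. The SAP's efficacy analyses address the first and not the second, and the SAP gives no reason for the difference.

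The practical consequence lies in the restricted subgroup. A subgroup of "patients who had not received azithromycin before randomization" removes one kind of prior exposure and keeps the other. If it showed little difference between arms, a reader could not tell whether the drugs perform alike or whether some comparator patients had already had part of a hydroxychloroquine course. Dilution of this kind moves the odds ratio toward 1, the direction that raises P5, the posterior probability the SAP reads as similarity between treatments.

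**Working it through.** **1. The texts side by side**

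| Item | Azithromycin | Hydroxychloroquine |
|---|---|---|
| Prior COVID-19 treatment allowed (Protocol 4.3, 5.2) | up to 2 days | up to 2 days |
| Exclusion for outpatient use in another disease (Protocol 4.3) | no | yes |
| Covariate in the sensitivity model (SAP) | yes | no |
| Defines the restricted subgroup (SAP) | yes | no |
| Exploratory subgroup (SAP) | yes, item (f) | no |
| Table 3 summary by arm, baseline to day 5 (SAP) | yes | yes |

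An azithromycin-arm patient with 2 days of prior hydroxychloroquine and no prior azithromycin is eligible, stays in the restricted subgroup, has a covariate value of zero in the sensitivity model, and falls on the unexposed side of item (f).

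**2. How much of a course 2 days could be.** The regimens are in Protocol 5.2.1 and 5.2.2. Assume the prior doses followed the study schedule.

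- Hydroxychloroquine: (800 + 400) / 2,400 mg = 50% of the course.
- Azithromycin: (500 + 250) / 1,500 mg = 50% of the course.

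The permitted maximum is the same share for each drug.

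**3. The plan's own power figures, as a base.** SAP Table 4 gives detectable odds ratios of 0.56, 0.55 and 0.55 at N=300 for Scenarios 1 to 3 (80% power, two-sided α = 0.05, 95% follow-up). I used the Whitehead approximation with 1:1 allocation, which is assumed because the documents do not state the ratio:

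- V = (n/12)(1 − Σ p̄³), with n = 0.95 × 300 = 285 and p̄ the mean of the two arms' category probabilities.
- Power = Φ(√V × |log OR| − 1.96).
- Scenario 3 at OR 0.55: Σ p̄³ = 0.035, V = 23.75 × 0.965 = 22.92, √V = 4.787, |log OR| = 0.598. Power = Φ(2.862 − 1.96) = 0.82.

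Power at the SAP's rounded odds ratios is 0.800, 0.791 and 0.817, and the formula's own detectable odds ratios are 0.560, 0.546 and 0.557. The plan's figures reproduce to within rounding.

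**4. Dilution, illustration only.** Let c be the share of the azithromycin arm with prior hydroxychloroquine and h the fraction of the full effect that those patients carry. Approximate the diluted effect by log OR* = log(0.55) × (1 − c × h), under Scenario 3 with N=300. For c = 10% and h = 0.5: −0.598 × 0.95 = −0.568, so OR* = 0.567.

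| Exposed share c | OR*, h = 0.5 | Power, h = 0.5 | OR*, h = 1 | Power, h = 1 |
|---|---|---|---|---|
| 0% | 0.550 | 0.82 | 0.550 | 0.82 |
| 5% | 0.558 | 0.80 | 0.567 | 0.78 |
| 10% | 0.567 | 0.78 | 0.584 | 0.73 |
| 20% | 0.584 | 0.73 | 0.620 | 0.63 |
| 30% | 0.602 | 0.68 | 0.658 | 0.52 |

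Both c and h are assumptions. The documents give neither. The columns for h = 1 are an outer bound, since the permitted exposure is at most half a course. The table describes the whole trial; the restricted subgroup is smaller, and its exposed share could differ.

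**The case against.** The strongest reply is that equal permission is not equal exposure. Outpatient hydroxychloroquine for other diseases is excluded. Protocol 3.1.3 says that azithromycin is commonly recommended with a beta-lactam for community-acquired pneumonia, which can be confused with COVID-19, so prior azithromycin is the foreseeable case. The SAP was written after enrollment began and adapts to what happened: it records that nobody entered under the suspected-disease criterion and that some hydroxychloroquine-arm patients received azithromycin. Its focus may simply reflect practice. That is plausible, and if prior hydroxychloroquine was nil the restricted subgroup would not change. But the SAP does not say so, and one sentence would settle it.

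Three stronger readings are tempting, and the documents do not support them:

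- **That hydroxychloroquine use in the azithromycin arm is ignored altogether.** It is not. Table 3 has it summarized by arm at baseline and through day 5, and the exploratory safety displays separate patients who received only azithromycin. The gap is in the efficacy analyses. The safety text does not name a group for azithromycin-arm patients who also took hydroxychloroquine.
- **That the SAP presents the restricted subgroup as free of contamination.** It gives no rationale for that subgroup and makes no such claim.
- **That the primary result is biased.** Prior exposure precedes randomization and is balanced in expectation, and the analysis is by assigned arm.

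It is also fair to object that adding prior hydroxychloroquine as a main-effect covariate would not undo dilution. The treatment coefficient would still average over exposed and unexposed patients; dilution would show as an interaction between treatment and prior exposure. That objection stands, and it makes the subgroup definition the useful change.

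**Conclusion.** The point holds as a small gap in the supporting analyses. The protocol admits patients with up to 2 days of either drug, and all three SAP efficacy analyses of prior exposure condition on azithromycin alone. Azithromycin-arm patients with prior hydroxychloroquine can therefore remain in the restricted subgroup, and no efficacy analysis addresses them.

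The size is unknown because no exposure rate is given. Under the stated assumptions it runs from nil, to little at 5% exposure (odds ratio 0.558 against 0.550 with half the effect), to modest at 30% (0.602). The figures rest on 1:1 allocation, scaling of the log odds ratio, and a true odds ratio equal to the plan's detectable value. The textual finding rests on none of these. The ITT primary analysis, its posterior thresholds and the sample size are unaffected.

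**What to change.** 1. In Analysis Sets, define the restricted subgroup as patients who received neither azithromycin nor hydroxychloroquine before randomization.
2. Report the number in each arm with prior hydroxychloroquine, or state that none occurred. If none did, that statement closes the point.
3. Optionally, add prior hydroxychloroquine to the sensitivity model for symmetry with azithromycin. The documents do not say that the amount was recorded, so an indicator of any prior use may be all that is possible. This term should not be presented as removing dilution.

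Hydroxychloroquine at baseline is already on the Table 3 list, so items 1 and 2 appear to need no new data. The cost is SAP wording and a somewhat smaller restricted subgroup, with correspondingly wider credible intervals.

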3.6 Secondary endpoints

Hospital-free days at 28 days (calculated as a worst-rank ordinal)

Ventilator-free days at 28 days (calculated as a worst-rank ordinal)

ICU-free days at 28 days (calculated as a worst-rank ordinal)

Time to a 1-point decrease in the WHO ordinal recovery score

The composite endpoints (-free days) will be calculated according to standard procedures (using the “last off” method) and using the worst-rank ordinal approach by which death is counted as -1 days.

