Secondary Analyses. We will apply similar Bayesian proportional odds models to evaluate the effectiveness of the hydroxychloroquine vs. azithromycin interventions for efficacy analyses of all ordinal outcomes. We will also present numbers (proportions) of patients in each ordinal status for all endpoints for descriptive purposes and to assist with future meta analyses. If the graphical diagnostics (described above) indicate that the proportional odds model is untenable for certain outcomes, we will report that fact, and supplement the primary analysis using the proportional odds model with separate logistic regression for different cutpoints or quantile regression in order to fully characterize the relationship of each outcome with treatment assignment.

Ordinal secondary outcomes include ventilator-, ICU-, and hospital-free days through day 28 (with death assigned as a worst-rank ordinal level^{5,6} to avoid survivorship bias for each of these outcomes). We will use the last-off method—only time after the last liberation from, e.g., ventilation counts toward the total number of -free days. Similar to the primary outcome measured at 14 days, we will apply a primary proportional odds model similar to that used for the primary analysis at day 14 to evaluate the effect of the randomized treatments on the COVID Ordinal Outcomes Scale at day 7. We will present the results of each of these analyses as the posterior median odds ratio with 95% credible interval under the moderately skeptical Bayesian prior described above. For ease of use for investigators performing meta-analyses, we will include detailed descriptions including number of patients for each value of the endpoints by treatment group as tables in the online supplement.

We include two time-to-event endpoints, censored at 28 days: time to a 1-point decrease in the COVID Ordinal scale and time to recovery (defined as in the ACTT-1 trial). The time to recovery endpoint was added after publication of the methods paper but before unblinding of investigators. It was added to assist with future meta analyses given increasing interest in it as an endpoint. Both time-to-event endpoints will be displayed by treatment group (for descriptive purposes) as Kaplan-HAHPs SAP

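### In the two time-to-event endpoints, deaths are tied with event-free survivors, so death is not ranked worst as the SAP says

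*SAP*

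**What the plan says.** All of the following is in the SAP, Secondary Analyses, unless another place is named.

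- On follow-up: "We include two time-to-event endpoints, censored at 28 days: time to a 1-point decrease in the COVID Ordinal scale and time to recovery".
- On deaths: patients who die before day 28 are "assigned an artificial follow-up time of 28 days censored at that point".
- On what this achieves: "This will assign to these patients a worse outcome than any surviving patients, and avoid conflating prolonged hospitalization with death".
- On the treatment effect for these endpoints: "we will use the same ordinal regression model with the same prior distribution" as in the primary analysis. The reported results are median posterior odds ratios and credible intervals. Kaplan-Meier curves are descriptive.
- On the free-day endpoints, for contrast: these are analysed "with death assigned as a worst-rank ordinal level". Protocol 3.6 likewise describes a "worst-rank ordinal approach by which death is counted as -1 days", which is strictly below zero free days.

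Protocol 3.6 lists time to a 1-point decrease but gives no rule for deaths on it. Time to recovery is defined in the SAP only by reference to another trial.

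**The concern.** The coding rule and its stated purpose do not agree. A survivor who reaches day 28 without the event is censored at day 28. A patient who dies earlier is also recorded as censored at day 28. Nothing in the data then separates the two.

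This reaches the inference as well as the plot. An ordinal regression sees only ordered categories, so equal values form one category. Any treatment effect that moves patients between death and event-free survival, in either direction, is invisible to the odds ratio. The trial report would meanwhile say that death had been ranked worst. The SAP added time to recovery to help later meta-analyses, whose users would rely on that description.

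**Working it through.** **Step 1: apply the rule to each type of patient.** This step needs no assumption.

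| Patient | Recorded time | Status |
|---|---|---|
| Event on day 5, survives | 5 | event |
| Event on day 28, survives | 28 | event |
| Survives to day 28 without event | 28 | censored |
| Dies on day 3 | 28 | censored |
| Event on day 5, dies on day 20 | 28 | censored |

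The third and fourth rows are identical. Deaths rank below survivors who had the event and level with those who did not.

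**Step 2: who the event-free survivors are.** For time to a 1-point decrease, the SAP (Primary Analysis) says "the baseline COVID Ordinal Outcomes Scale distribution will include only patients with levels 3 through 7". In Protocol 3.5, Table 1, levels 3 to 7 are all hospitalized states and 8 is death, so a living patient outside hospital scores 1 or 2. Starting from 3 or more, discharge is itself a decrease of at least one point. A survivor with no such decrease by day 28 has therefore not left hospital. The tie for this endpoint is between prolonged hospitalization and death, which is the conflation that the SAP says it avoids. For time to recovery the definition is not in the documents, so only the tie with event-free survivors can be stated.

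**Step 3: size.** The plan attaches no figure to this point, so there is none to reproduce. The following is an illustration.

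*Inputs from the documents:* 300 randomized (SAP, Sample size and power); prior for the log odds ratio normal with mean 0 and SD 0.354 (SAP, Primary Analysis); 16% dead, which is the day-14 figure in Scenario 2.

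*Assumptions:* 150 per arm; four event-time categories in the ratio 0.30 : 0.30 : 0.09 : 0.05; a control share *e* of event-free survivors, varied because the documents do not give it; no covariates.

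*Method:* a proportional odds model was fitted by maximum likelihood to the expected counts, once with death as its own last category and once with death merged with event-free survivors. For a log odds ratio *b* with standard error *s*, the posterior has variance v = 1/(1/s² + 1/0.354²) and mean m = v·b/s², so P(OR<1) = Φ(−m/√v). An odds ratio below 1 favours hydroxychloroquine.

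| Deaths, control to treated | *e* | Averted deaths become | OR, death separate | OR, tied |
|---|---|---|---|---|
| 16% to 8% | 2% | all event-free survivors | 0.954 | 1.000 |
| 16% to 8% | 10% | all event-free survivors | 0.936 | 1.000 |
| 16% to 8% | 30% | all event-free survivors | 0.889 | 1.000 |
| 16% to 8% | 2% | spread over survivors in proportion | 0.768 | 0.773 |
| 16% to 8% | 10% | spread over survivors in proportion | 0.773 | 0.795 |
| 16% to 8% | 30% | spread over survivors in proportion | 0.775 | 0.841 |
| 8% to 4% | 10% | all event-free survivors | 0.977 | 1.000 |
| 8% to 4% | 10% | spread over survivors in proportion | 0.878 | 0.890 |

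In the harmful direction, with deaths rising from 16% to 22%, event-free survivors falling from 10% to 4% and events equal, the odds ratio is 1.051 separate against 1.000 tied.

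**Step 4: after the prior.** The standard error of the log odds ratio is about 0.21. Take deaths 16% to 8%, *e* = 10%, all averted deaths event-free and death separate. Then b = ln 0.936 = −0.066 and s = 0.206, so 1/s² = 23.6 and 1/0.354² = 8.0. This gives m = −0.066 × 23.6/31.6 = −0.049, a posterior median of 0.952 and P(OR<1) = 0.61. Tied, the values are 1.000 and 0.50. With proportional spread, the posterior medians are 0.826 separate and 0.844 tied, and P(OR<1) is 0.86 and 0.83.

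**The case against.** The strongest reply is that the 28-day censoring rule sits beside the Kaplan-Meier description and uses survival-analysis terms, while the sentence on ordinal regression states no coding for deaths. Some translation into categories is needed. The declared intent is that death be worst, and the free-day endpoints show the trial's habit of giving it a worst rank. A programmer might well have done the same here. That is possible, but no text says so. The free-day endpoints show that the SAP names a separate level when it wants one. If a separate level was meant, writing it down costs nothing.

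Second, holding deaths event-free to day 28 is a usable coding for time to improvement. This is accepted for the curves. The fault is in claiming a ranking that this coding does not produce.

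Third, the effect is small. The SAP reports posterior medians, which the prior pulls toward 1. Having every averted death become an event-free survivor is an extreme case. For the 1-point endpoint, the event-free share may lie at the low end of the range, where proportional spread gives posterior medians of 0.823 and 0.826. The 95% and 75% thresholds are set for primary inference, so no decision rule is tied to these endpoints. Deaths also remain visible in the primary outcome, in the free-day outcomes and in the supplementary tables. All of this stands and limits the importance of the point. It does not make the sentence true.

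**Conclusion.** The concern holds. As written, deaths and event-free survivors share one value on both time-to-event endpoints. The statement that death is worse than every survivor's outcome is therefore false for event-free survivors. This follows from the text alone.

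The numerical effect is probably modest. At 16% versus 8% deaths and 10% event-free survivors, the odds ratio differs by about 0.02 under proportional spread (0.773 against 0.795) and by about 0.06 in the extreme case (0.936 against 1.000). At 30% event-free survivors the differences grow to about 0.07 and 0.11. These sizes depend on the assumed death rates, event-free share and event-time shape, and on an unadjusted fit. In none of the cases for which a posterior was computed does P(OR<1) reach 95%.

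Only these two secondary endpoints are involved. The primary endpoint scores death as 8, the free-day endpoints give it its own lowest level, and neither is affected. It should be corrected before analysis.

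**What to change.** In the ordinal regression for both endpoints, place deaths by day 28 in their own category beyond event-free survivors, for example time 29 with event-free survivors left at 28. If the model reads only the numeric time, an event on day 28 must also stay distinct from event-free survival; levels 28, 29 and 30 would do this.

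Keep the 28-day censored coding for the Kaplan-Meier display only. Amend the sentence in Secondary Analyses to say that death ranks worst in the ordinal model, and that in the curves deaths are held event-free to day 28. State how a death on day 28 itself is coded, since the present rule covers only earlier deaths.

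The cost is a recoded value and an amended passage in the SAP. No new data are needed.

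### Exploratory effect variation by age and symptom duration rests on single cutpoints, and no interaction estimate is specified for the final analysis

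*SAP*

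**What the plan says.** The SAP, Sub-groups, labels this work purely exploratory and states that "we will summarize effect variation in sub-groups defined by (a) age". Age is the first of six factors. Age (65 years or more) and symptom duration (10 days or more) are numeric variables cut at one point. The others are ICU status at enrolment, any comorbidity, race/ethnicity and prior clinical azithromycin.

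The only method in that paragraph concerns early interim analyses, where "we will limit presentation of results in sub-groups to descriptive summaries". For the final analysis it names no model, contrast or interval.

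Under Analysis Sets, the SAP adds that in part of the ITT population "we will compare study endpoints among patients who had not received azithromycin before randomization". No contrast with the remaining patients is named there.

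Under Primary Analysis, the covariates begin: "Patient age, comorbidities (dichotomized as either no comorbidities or any comorbidities". Dichotomizing is stated for comorbidities. The form in which age enters is not stated. Symptom duration is not in the model.

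Other efficacy reporting is specific. The ordinal secondary outcomes, for example, are to be given as the "posterior median odds ratio with 95% credible interval".

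**The concern.** The quantity that measures effect variation is a contrast: how much the treatment odds ratio changes with the modifier. The SAP states that it wants effect variation but does not name this quantity. Two separate problems follow.

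- **Cutting costs power.** Replacing years of age, or days since onset, by a yes/no split discards information about a gradient, so a real trend is more likely to be missed.
- **No contrast invites misreading.** If the final report shows only an odds ratio for each side, readers will compare them by eye. One side can look convincing and the other not when the effect is the same in both. This applies to all six factors, not only the two that are cut.

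At stake is the reading of the exploratory results and their use in later meta-analyses, which both documents anticipate.

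**Working it through.** **Inputs.** From the SAP: 300 randomized, 95% follow-up, 80% power, two-sided 0.05 (Sample size and power, Table 4); Scenario 3 as the average of Scenarios 1 and 2, which gives 0.0625, 0.2425, 0.1425, 0.1775, 0.0875, 0.0725, 0.0725, 0.1425; prior SD 0.354 for the log odds ratio and the 95% threshold for P1 (Primary Analysis). Analysed patients: 300 × 0.95 = 285. Assumed, because the documents do not give them: 1:1 allocation, the share of patients above each cut, the shape of each modifier, and a linear modification.

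**1. The plan's own figure.** The SAP gives no figure for sub-groups, so Table 4 is the check. Whitehead's formula is N = 12(1.960 + 0.842)² / [ln(OR)² × (1 − Σp̄³)], where p̄ is the mean of the two groups' category probabilities. With N = 285 it gives detectable odds ratios of 0.560, 0.546 and 0.557 for Scenarios 1 to 3. Table 4 states 0.56, 0.55 and 0.55, so it reproduces. The matching standard error of the log odds ratio is √{12 / [285(1 − Σp̄³)]}. At OR 0.60 under Scenario 3, Σp̄³ = 0.0337 and the standard error is √(12/275.4) = 0.209.

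**2. Information lost by one cut.** For a normal modifier with share p above cut c, the fraction kept on a linear trend is k = φ(c)² / [p(1 − p)]. An interaction that has 80% power when kept continuous then has power Φ(2.80√k − 1.96).

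| Share above cut | φ(c) | Kept | Lost | Power (80% if continuous) |
|---|---|---|---|---|
| 20% | 0.280 | 49% | 51% | 50% |
| 30% | 0.348 | 58% | 42% | 57% |
| 40% | 0.386 | 62% | 38% | 60% |
| 50% | 0.399 | 64% | 36% | 61% |

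The loss is smallest, 36%, at a median split. Simulating the ordinal model (1,000 runs, Scenario 3, 285 patients) gave losses of about 49%, 41% and 38% at shares of 20%, 30% and 50%. Assumed age means of 50 to 65 with SDs of 13 to 17 give 36% to 61%. Uniform, exponential and gamma shapes give 25% to 52% at shares of 20% to 50%.

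**3. Chance differences between strata.** Assume one common odds ratio, so there is no true variation. A stratum holding share p has standard error s = SE/√p. With prior SD 0.354, w = 0.354² / (0.354² + s²), and P1 reaches 95% when the estimated log odds ratio is below −1.645 s/√w. Example at OR 0.60 (log −0.511) and p = 20%:

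- small side: s = 0.467, limit −1.270, probability Φ[(−1.270 + 0.511)/0.467] = 0.052;
- large side: s = 0.233, limit −0.460, probability Φ[(−0.460 + 0.511)/0.233] = 0.587;
- exactly one side: 0.052 × 0.413 + 0.587 × 0.948 = 0.58.

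| Common OR | Exactly one side reaches P1 ≥ 95% (shares 20% to 40%) |
|---|---|
| 0.60 | 47% to 58% |
| 0.70 | 30% to 34% |
| 0.80 | 15% to 17% |
| 1.00 | about 3% |

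A measure that needs no threshold uses the standard error implied by Table 4, −ln(0.55)/2.80 = 0.213, and no prior. The two odds ratios then differ more than 1.5-fold by chance in 34% to 45% of trials (shares 50% down to 20%), whatever the common odds ratio. A contrast tested at 0.05 is falsely positive in 5%; six independent contrasts give at least one in 1 − 0.95⁶ = 26%.

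**4. What a contrast can show here.** For a binary split the standard error of the log ratio of odds ratios is 0.213/√[p(1 − p)], which is 0.533 at 20% and 0.427 at 50%. The ratio detectable with 80% power is therefore exp(−2.80 × 0.533) = 0.22 to exp(−2.80 × 0.427) = 0.30. For a continuous modifier it is about exp(−2.80 × 0.208) = 0.56 per SD. At 0.80 per SD, power is about 19%.

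**The case against.** The strongest reply is that the paragraph is labelled exploratory, that no decision, stopping rule or primary claim depends on it, and that the SAP itself calls early sub-group samples too small for inference. All of that stands and keeps the point minor.

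Four stronger readings are tempting, and the documents do not support them.

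- **That the SAP excludes a between-group contrast.** It is silent for the final analysis, and effect variation could include one. Only early interim analyses are limited to description.
- **That cutting discards a fixed 40% to 50%.** No distribution of age or symptom duration is given. For a normal modifier that range needs roughly 21% to 34% (or 66% to 79%) of patients at or above the cut. Days since onset cannot be negative, so normality is doubtful there. If the effect steps at the cut, the linear term is the less efficient choice.
- **That cutting makes chance differences look like effect modification.** Cutting lowers power for a trend. The misreading comes from comparing strata without a contrast and would affect ICU status or race/ethnicity equally.
- **That about half of trials would show a false contrast.** This needs a large common effect, near the design's detectable 0.55, and a threshold the SAP sets only for primary inference. At a 20% share, much of the discordance is the small stratum rarely crossing (5% against 59%).

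Nor does the SAP say that age enters the primary model undivided; that is an inference from its wording on comorbidities. Finally, continuous terms would not make this trial well powered for modification, as step 4 shows.

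**Conclusion.** The point holds as a cheap improvement to an exploratory analysis. The SAP chooses single cutpoints for two numeric modifiers and leaves the measure of effect variation unnamed for the final analysis. Under a normal modifier and a linear gradient the cut costs at least about 36% of the information on the trend; other shapes give roughly 25% to 52%. The chance of discordant strata ranges from about 3% with no effect to 47% to 58% at a common odds ratio of 0.60, and is illustrative only. The primary inference is not affected.

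**What to change.** Keep the exploratory label and keep the sub-group tables as display. Add to the Sub-groups paragraph, for the final analysis:

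- one model on all patients with a treatment-by-age term (years) and one with a treatment-by-symptom-duration term (days), both continuous;
- interaction terms for factors (c) to (f), with a set of terms for race/ethnicity if it has more than two levels;
- each ratio of odds ratios with its 95% interval (for age, per 10 years), naming any prior placed on the interaction coefficient;
- a sentence that effect variation is read from these estimates and that their precision is low.

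The cost is one paragraph and a few extra fits. No new data should be needed, since the planned splits already require age and symptom duration. The downside is that a linear term is less efficient if the effect steps at the cut; the retained sub-group display would help to reveal that.
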